TITLE: Randomized Trial of Peer-to-Peer Versus Pharmacist Education to

Improve Older Adults' Vaccination Knowledge Through the Senior Center Model of Care

CLINICALTRIALS.GOV

NCT NUMBER

NCT03239665

May 1, 2017 DOCUMENT DATE:

Merck Investigator Studies Program (MISP) Protocol Template

Requirements for Submitting a Full Proposal

Section #1 - MISP Protocol Identification

Study Title:	Randomized Trial of Peer-to-Peer Versus Pharmacist Education to Improve Older Adults' Vaccination Knowledge through the Senior Center Model of Care	
Request Date:	May 2, 2016	
Institution Name	Rutgers University	
Investigator Contact Information: □ Full address □ Phone No. □ Fax No. □ e-mail address	[name], MPH Professor, Department of Pharmacy Practice Rutgers University [name] [contact] [contact] [contact]	

Section #2 - Core Protocol

The main goal of this project is to conduct a randomized trial to compare the efficacy and costs of two interventions to improve knowledge and beliefs regarding vaccine-preventable diseases. The interventions tested will be delivered to older adults in the Delaware Valley region using a senior center model of care and will compare a pharmacist-led didactic teaching (PHARM) to peer-to-peer teaching (PEER). The project will be conducted by Rutgers University in partnership with Thomas Jefferson University (TJU) and Center in the Park (CIP). CIP is a nationally-accredited senior center which has been recognized by the National Institute of Senior Centers (NISC) for its commitment to wellness and evidence-based health promotion. PHARM and PEER will be targeted towards African American (AA) communities and will address major vaccine-preventable diseases. Intervention content will be focused on zoster and pneumococcal infections but will compare and contrast influenza to these diseases to further participants' understanding of the differences between these diseases and vaccination recommendations.

2.1 Objectives

- Compare the efficacy of PHARM vs. PEER at improving participant's knowledge regarding vaccine-preventable diseases
- Compare the efficacy of PHARM vs. PEER at improving participants' beliefs about vaccination
- 3) Measure the costs of PHARM and PEER from the senior center perspective
- 4) Compare the percent of participants taking activation step(s) to get vaccinated following receipt of PHARM vs. PEER
- 5) Determine the extent to which participants are satisfied with and trust the PHARM vs. PEER interventions

2.1.1 Hypotheses

- PHARM and PEER will achieve similar improvements in older adults' knowledge of vaccine preventable diseases (primary hypothesis)
- PHARM and PEER will improved beliefs about vaccinepreventable disease
- 3) **PEER will be a lower cost approach** to educating participants in the senior center compared to PHARM
- 4) PHARM and PEER will result in similar rates of participants taking one or more activation step(s) to obtain vaccination
- 5) Participants will be highly satisfied with the PHARM and PEER interventions

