Intervention costs for PHARM and PEER will be calculated as the monetary value of time and materials required to train involved personnel, and deliver PHARM and PEER as well as personnel travel costs. Data on personnel time requirements for delivering PHARM and PEER will be collected in real time by

trained staff members using time logs which document the time and staff members required for training and delivery of the program. These data will be monetized using the hourly wage rates plus fringe benefit costs of the involved personnel. Other costs include materials such as signage, a modest participant giveaway such as medication reminder cards and pill box, printing/duplication, and food/refreshments. All costs will be reported in \$US 2017, consistent with the intervention time period.

Activation (Objective 4):

Participant activation will be measured as percent of participants who report taking one or more actions towards receiving vaccination at one month post-intervention, such as discussion with a healthcare provider (physician/pharmacist) or friends/family and/or receiving vaccination for either pneumonia or zoster. For participants who report vaccination, we will report which (pneumonia, zoster, or both). Influenza vaccination activation will be excluded from this measure since influenza vaccination is widely promoted through other initiatives which could influence activation, such as onsite flu shots at CIP.

Satisfaction (Objective 5):

Satisfaction measures will include **participants' overall satisfaction** with the content and delivery of PEER vs PHARM, the extent to which the participant felt **engaged**, and their **satisfaction with information received**. Satisfaction will be measured only at post-test using a simple 5-10 item satisfaction survey adapted from our prior research.

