2.7.3 Sample Size Justification

The sample size was calculated using G*Power 3.0.10 and is based on the primary outcome measure (difference between change in mean knowledge score from baseline to 1 month for PHARM vs PEER). We plan to use a two-tailed independent samples t-test with α =0.05 to determine the between-group difference in mean knowledge scores at each timepoint. We seek to examine the difference, if any, in the effectiveness of the two approaches, PHARM and PEER; specifically, we wish to determine if the two approaches have similar results to within 20% difference expecting large variability (50% standard deviation). This difference is detectable at a power of 0.8 with 121 participants in each arm of the study. To ensure an adequate sample size, we scaled up the sample size calculation using the attrition rate from the prior pneumonia project. Attrition rate in PPPP was $\frac{203-143}{203}$ =0.296 ≈30%; thus scaling up by 30% yields a total sample size of 316 (158 in each arm).

As a secondary outcome, consistent with the prior pneumonia project, we plan to use a two-tailed paired samples t-test to determine the within-group difference in mean knowledge score between timepoints. However, because within-group differences are easier to detect than between-group differences, the sample size is powered to detect the 20% between-group difference.

2.8 Specific Drug Supply Requirements	None – vaccination is not included as a component of this study.	
2.9 Adverse Experience Reporting	Not required since vaccination is not being offered through this study.	
2.10 Itemized Study Budget	Provided as attachment.	

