The number of correct responses to the knowledge items at each timepoint was calculated as a whole and by disease (pneumonia, influenza, zoster). Baseline knowledge was compared by race via Kruskal-Wallis test. Because the knowledge data were expected to be non-normal and integer-valued, knowledge items were assessed using nonparametric methods. Specifically, between-group differences in knowledge were assessed at each timepoint via Wilcoxon Rank-Sum test. Similarly, between-group knowledge differences across timepoints were assessed pairwise via Wilcoxon Rank-Sum tests with Bonferroni-corrected significance threshold of

 α =0.05/3=0.0167. Within-group differences in knowledge score across timepoints were tested pairwise using Wilcoxon Signed-Rank tests.

Beliefs

The percentage of respondents answering "Completely Agree" to each item at each timepoint was calculated and compared between PHARM and PEER, as in our PPPP study. Pairwise Wilcoxon Signed-Rank tests were run comparing within-group changes in beliefs across timepoints applying Bonferroni correction (α =0.05/3=0.0167). Either Chi-Square or Fisher's Exact tests were used to compare beliefs between groups at each timepoint, depending on expected cell counts.

Activation

For all participants, Chi-Square or Fisher's Exact testing was performed as appropriate at each timepoint to assess between-group differences in proportions of participants planning actions, including planning vaccination and planning to speak with a doctor, pharmacist, or family/friends, as well as actions taken, including vaccinations obtained and having spoken with a doctor, pharmacist, or family/friends.

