For participants who did not report positive vaccination status on the post-intervention survey, Chi-Square or Fisher's Exact testing was performed on PT & M1 data for each vaccine type to test for differences between PHARM and PEER with significance level α =0.05. The PT response to the vaccination items was chosen instead of the BL response because it was felt that the responses to these items would be more reliable and accurate after having received the intervention as compared to baseline, when participants may have had a less clear ability to differentiate between the vaccines they may have received. For survey items pertaining to plans/actions related to vaccines, participants not reporting positive vaccination status were compared between PHARM and PEER at each timepoint for item (discussion with doctor, pharmacist, or family/friends) via Chi-Square or Fisher's Exact tests as appropriate.

Satisfaction

For both PT and M1, proportions of respondents answering favorably ("Completely Agree" or "Somewhat Agree") and unfavorably ("Completely Disagree" or "Somewhat Disagree") to the two satisfaction items (program satisfaction and program engagement) were compared between PHARM and PEER using either Chi-Square or Fisher's Exact test as appropriate.

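### Hypothesis 4 predicts similar activation rates, but the plan compares activation only with tests for a difference and so cannot answer it

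*Protocol*

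**What the plan says.** Hypothesis 4 (Protocol 2.1.1) is a similarity claim about a proportion: "PHARM and PEER will result in similar rates of participants taking one or more activation step(s) to obtain vaccination". Protocol 2.7.2 defines the outcome as the "percent of participants who report taking one or more actions towards receiving vaccination at one month post-intervention".

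The one place that puts a number on closeness is Protocol 2.7.3: "we wish to determine if the two approaches have similar results to within 20% difference". That calculation "is based on the primary outcome measure (difference between change in mean knowledge score from baseline to 1 month for PHARM vs PEER", so the 20% does not carry over to activation. No activation rate, margin, power or precision is given in either document.

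For the analysis, the SAP (Activation) says: "For all participants, Chi-Square or Fisher's Exact testing was performed as appropriate at each timepoint to assess between-group differences in proportions". For participants who had not reported vaccination at post-test it again specifies Chi-square or Fisher tests, "to test for differences between PHARM and PEER with significance level α =0.05". No risk difference, confidence interval or similarity rule appears. The SAP overview lists activation among the secondary measures, places randomization at the program date, and fills missing one-month data from the post-test or baseline.

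**The concern.** The hypothesis and the test point in opposite directions. A Chi-square or Fisher test takes equal rates as its null, so a small p-value speaks against Hypothesis 4 while a large one shows only that a difference was not detected. Under the plan as written, the only result that could be read in favour of Hypothesis 4 is a non-significant p-value, and neither document says how such a result will be interpreted.

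This bears on how the trial would be used. Protocol 2.7.2 (Cost Analysis) gives the main reason for measuring cost as learning whether the programs are cheaper with comparable efficacy. Activation, which includes vaccination itself, is one of the outcomes on which a reader would judge comparability. A shortfall in one arm could go unreported because the plan yields no estimate with its uncertainty.

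**Working it through.** **The plan's own figure.** Protocol 2.7.3 gives 121 per arm for the knowledge score (20% difference, 50% SD, two-sided 0.05, 80% power), raised to 158. The usual formula gives 2 × (1.96 + 0.842)² × (50/20)² = 98.1, so 99 per arm (100 for the t-test); 121 has 87% power and is reproduced only with a two-sided alpha of 0.025. The 158 is 121 × 1.3 = 157.3, rounded up. This concerns knowledge and neither supports nor weakens the present point. It does supply the sizes to use: 121 per arm (planned evaluable) and 158 per arm (enrolled, and the analysed number if every missing value is carried forward).

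**Chance that a true gap is non-significant.** Assumed: the PHARM rate p1; PEER lower, p2 = p1 − 0.10; independent participants; two-sided 0.05. With p̄ the mean of the two rates,

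power ≈ Φ{[0.10·√n − 1.96·√(2p̄(1−p̄))] / √(p1(1−p1) + p2(1−p2))}.

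For 50 v 40% at n = 158: (1.257 − 1.379)/0.700 = −0.174, so power is 43% and the miss rate 57%. Exact binomial enumeration of the uncorrected Chi-square test gives:

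| PHARM v PEER | Missed, 158 per arm | Missed, 121 per arm |
|---|---|---|
| 20 v 10% | 29% | 40% |
| 35 v 25% | 51% | 60% |
| 50 v 40% | 58% | 66% |
| 70 v 60% | 53% | 62% |
| 80 v 70% | 46% | 56% |
| 90 v 80% | 29% | 40% |

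For a 15-point shortfall at 158 per arm and PHARM rates of 35% to 70%, the miss rate is 15% to 24%.

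**Precision.** With a common rate p, the 95% half-width is 1.96·√(2p(1−p)/n). For p of 35% to 70% this is 10.1 to 11.0 points at 158 and 11.6 to 12.6 at 121, or about 10 to 13 points.

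**Clustering.** Assumed: ICC 0.01 to 0.05 and 25 to 55 people per program date (the PHARM session sizes in Protocol 2.5, applied to both arms). The design effect 1 + (m − 1)·ICC runs from 1 + 24 × 0.01 = 1.24 to 1 + 54 × 0.05 = 3.70. At p = 50%, the half-width runs from 11.03 × √1.24 = 12.3 points (158 per arm) to 12.60 × √3.70 = 24.2 points (121 per arm). It reaches 25.3 at 111 per arm, which is 158 after 30% loss (158 × 0.70 = 110.6). With only 3 or 6 PHARM sessions planned, the multiplier 1.96 is itself optimistic.

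**What a margin would imply.** The approximate chance that a 90% interval lies inside ±m when the true rates are equal is 2Φ(m/SE − 1.645) − 1. At p = 50% and n = 158, SE = √(0.5/158) = 0.0563. A 10-point margin gives 2Φ(0.133) − 1 = 11%, and a 20-point margin 2Φ(1.911) − 1 = 94%. At a 90% rate, the 10-point figure is 81%. Clustering is ignored here and would lower all of these.

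**The case against.** Several points on the other side stand.

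- **The miss rate is conditional.** A reader might infer that a 10-point gap would be missed at least half the time. The documents give no activation rate, so they do not support that as a general statement. Because the outcome counts any one step, including a talk with family or friends, a high rate is plausible. At 158 per arm the miss rate is below one half for 80 v 70%, 90 v 80% and 20 v 10%.
- **A shortfall would not usually pass as support.** A reader might also infer that a real deficit in PEER would most often look like agreement with Hypothesis 4. For 15 points at 158 per arm the miss rate is only 15% to 24%, and neither document says what gap would matter.
- **No misuse is announced.** Neither document says that a non-significant result will be called similar. The defect is that nothing else is provided.
- **Activation is secondary.** The primary hypothesis concerns knowledge, and low power on a secondary outcome is not in itself an error.
- **The tested items differ from the composite.** The SAP lists planned and taken actions separately, does not name the one-or-more composite of Protocol 2.7.2, and limits some tests to participants not reporting vaccination. The figures above apply the SAP's test to the protocol's outcome; individual items and the subgroup would have their own rates and numbers.

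None of this supplies a margin, an interval or a rule for concluding similarity.

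**Conclusion.** The point holds as a mismatch between hypothesis and analysis: a secondary similarity hypothesis has no criterion, and the only tests applied to it can count against it but never for it. That conclusion rests on the text alone and does not depend on an activation rate.

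The numerical size does. For assumed PHARM rates of 35% to 70%, a true 10-point shortfall in PEER is missed about 51% to 58% of the time at 158 per arm and 60% to 66% at 121. At 80 v 70% the figures are 46% and 56%, and at 90 v 80% or 20 v 10% they are 29% and 40%. All assume independent participants; accounting for randomization by program date would raise them. The 158-per-arm figures also treat carried-forward values as if they were observed at one month.

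The point merits a change to the SAP but does not touch the primary comparison.

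**What to change.** In SAP Activation, name the Protocol 2.7.2 outcome (at least one activation step by one month) as the measure for Hypothesis 4. Report the PHARM minus PEER risk difference with a 95% confidence interval that accounts for randomization by program date, by a method suited to few dates. State that a non-significant Chi-square or Fisher p-value will not be reported as similar.

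Reword Hypothesis 4 as estimation of the difference. Do not write in an expected half-width of 10 to 13 points, because that figure assumes independent participants.

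If the similarity claim is kept, justify a margin in percentage points without reference to the results, state the interval level, require the interval to lie wholly inside the margin, and otherwise report the result as inconclusive. The SAP is dated March 2020 and written in the past tense, so a margin set after the data were seen must be labelled post hoc.

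The cost is a few sentences and one adjusted estimate from data already planned; no more participants are needed. The downside is that Hypothesis 4 will probably be reported as inconclusive for modest gaps.

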2.1 Objectives & Hypotheses

2.2.1 Background and Rationale

Vaccination is the single best way to prevent common infectious diseases in older adults, including those caused by pneumococcus, zoster, and influenza. Though influenza vaccination programs are widespread, programs targeting pneumococcal and zoster infections are fewer. According to the Centers of Disease Control and Prevention (CDC), many adults remain unvaccinated for these diseases, including those at the highest risk of infection. For example, in 2013 the CDC estimated that only 59.7% of adults 65 years and older had ever received a pneumococcal vaccination. In Pennsylvania the estimates are considerably lower. According to a 2004 Southeastern Pennsylvania Household Health Survey, only 51.9% of adults over 60 had ever received a pneumococcal vaccination. Furthermore, only 43.6% of the poor have ever had a pneumococcal vaccination and only 41.6% of African Americans (AA) have ever received a pneumococcal vaccination compared to 53.6% of Caucasians.² These values indicate concerning disparities in pneumococcal vaccination between AAs and whites.3 These disparities could be exacerbated by increased complexity of pneumococcal disease vaccination quidelines; the Advisory Committee on Immunization Practices (ACIP) now recommends that older adults receive two different pneumococcal (pneumococcal conjugate vaccine vaccinations and pneumococcal polysaccharide vaccine). 4

2.2 Background & Rationale, Significance of Selected Topic & Preliminary Data

There are similar population health concerns pertaining to zoster. Nearly one-third of people will experience a zoster infection, i.e., shingles, in their lifetime.⁵ Many will also experience ongoing sequelae of zoster such as post-herpetic neuralgia or ocular damage, both of which may interfere with activities of daily living. 6,7 Despite demonstrated efficacy. Food and Drug Administration Approval and ACIP recommendations, many patients eligible for the zoster vaccine have not received it. According to the CDC, in 2013, 24.2% of adults aged ≥60 years old reported receiving zoster vaccination to prevent shingles, an increase from the 20.1% in 2012.8 While improved, the proportion of eligible adults receiving the herpes zoster vaccine remains below the Healthy People 2020 target of 30%.9 Further, while whites aged ≥60 years had higher rates of zoster vaccination (27.4%) African Americans (10.7%) and Hispanics (9.5%) had considerably lower rates. To further understand zoster educational needs, we conducted a survey of Philadelphia senior center members in 2015. Findings confirm an unmet educational need for zoster education at the local level (see Appendix). These zoster data, considered together with similarly concerning pneumococcal vaccination data, reflect a critical need to educate older adults to improve vaccination rates and reduce health disparities among minority populations.

2.2.2 Significance of Selected Topic

Because vaccination rates among older adults are suboptimal, new models of care are needed. The senior center model of care uses a community-based senior center as the focal point of access to an older population and provides preventative health services through a facility the population already attends. Through our prior work, Jefferson and Center in the Park

have demonstrated that **senior centers can be an effective**, **engaging**, **and accessible hub for health promotion**. These efforts have included a depression support program, glaucoma detection program, diabetes adherence intervention, and pneumonia education and vaccination (described below under Preliminary Data). 10-17

The proposed topic is significant because it will further our prior work to vield effective, sustainable and scalable interventions to educate older adults about vaccination. Though a prior intervention we tested (pharmacist-delivered pneumonia intervention) significantly improved vaccination knowledge, beliefs, and activation, the economic analysis of that program revealed that it is resource intensive and costly (\$119/participant). In fact, our implementation experience suggests that the intervention was cumbersome (required 3 components: pharmacist-delivered presentation, live actors skit, and pharmacist-led breakout sessions) and too time consuming for participants (approximately 3 hours of time required to attend the session). Older adults who participated in the study were cooperative, but the amount of time required made it challenging to coordinate with senior group calendars. Further, there were space **limitations** at some sites which were exacerbated by the intervention's significant staffing requirements (mean staff requirements per session were 3.6 pharmacists, 8.0 actors, 5.5 student assistants, and 2.0 community health workers).

This points to the need for simpler, shorter, and cheaper vaccine education programs to be delivered using senior center models. In the proposed study, we will compare the efficacy of the main components of the prior pneumonia intervention; pharmacist-led education compared to peer-to-peer education (e.g., role play exercises which are an adaptation of the live skit). We hypothesize that both interventions will improve vaccination knowledge, beliefs, and activation, but that the peer to peer intervention will be less costly than the pharmacist-led education. Given the tendency to consult with and trust peers regarding healthcare concerns. peer-to-peer education has long been recognized as a potential source of health promotion within communities. This has been particularly true among those that have inconsistent engagement with the healthcare system. Perhaps the most widely documented health promotion interventions have occurred within the African American population at venues that serve as cultural and/or religious centers of the community. 18 For example, African American owned barbershops represent cultural institutions that serve a loyal group of male patrons and that provides a forum for peers to openly discuss contemporary and relevant topics. Regarding health, these community venues have served as locations for successful peer to peer health promotion programs on hypertension, diabetes, depression, HIV/AIDS, sexually transmitted diseases and cancer among others.¹⁹

